7 DATA COLLECTION AND MANAGEMENT PROCEDURES

7.1 Data collection

Participants will complete 3 data collection appointments. Each appointment will last approximately 90 minutes and will consist of a survey assessment, an HbA1C test, and two blood pressure readings. Participants enrolled prior to AME00101220 were enrolled in-person and completed surveys and assessments in-person; following AME00101220 all surveys and assessments for all participants are conducted virtually via phone. The baseline survey will be

given to participants prior to randomization. At the baseline appointment participants randomized to the intervention group will be asked to engage with the CareAvenue website on a tablet provided for use on-site or on own personal devices for virtual appointments. They will be asked to complete the website, which will take up to 20 minutes, and will also be provided a unique username and ID to login to the website on their own time.

Trained research staff will collect survey data via a computer-assisted interview through the use of Qualtrics software. We will assess HbA1c with an HbA1c machine. For in-person appointments research staff will be trained in best practices for HbA1c assessment by staff of the University of Michigan Department of Pathology. Once trained, research staff can train additional staff on use of the HbA1c machine. The HbA1C reading will be entered into Qualtrics. We will take the participant's blood pressure readings using an automatic blood pressure monitor. The blood pressure readings will also be entered into Qualtrics. Participants completing virtual appointments will obtain these measurements using at-home testing supplies provided by the study team.

All data will be downloaded from Qualtrics into a CSV file. This file will then be uploaded into SAS to create the study database.

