7.2 Process evaluation

On a regular basis once the intervention is deployed, a research staff member will monitor resources being promoted. We will measure program engagement by completed IVR calls and web analytics data (e.g. unique log-ins, time on page, click throughs, etc).

We will also assess experience with the program with a purposive sample of intervention participants selected based on differing levels of engagement with the intervention.

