8.2 Regression models

For the primary outcome (HbA1c), we will fit a longitudinal mixed-effects model to all repeated measurements during the pre-randomization baseline period and the one-year intervention period. The model will have the intervention (yes/no) as the main independent

variable and HbA1c accounted for as a repeated measure within patients. Thus, we will model HbA1c as a function of fixed effects for the treatment arm (the intervention group vs. the control group), the observation period (baseline vs. one-year intervention period), and a treatment-by-time period interaction term, with adjustment for confounding covariates (age, gender, race, income, health insurance type, comorbidities, health literacy). For this model, the coefficient of the treatment-by-time period interaction effect estimates the key parameter of interest: changes in HbA1c levels. Random effects are included in the model to adjust for HbA1c variation over time within patients. We will take a similar modeling approach to secondary outcome measures (CRN behaviors, perceived financial burdens, perceived stress of unmet SDHs). We will also dichotomize outcomes based on standard thresholds (eg., baseline HbA1c 8-9% vs > 9%) and use similar mixed-effects logistic regression models to test differences in HbA1c, CRN behaviors, perceived financial burdens, and perceived stress of unmet SDHs across treatment arms.

Among those randomized to CareAvenue in Aim 1, we will assess the change in magnitude of the outcome coefficient's association with the intervention before and after the adjustment of mediators of interest (see Figure 1, conceptual model). We will examine the Lagrange Multiplier and Wald Tests to consider the deletion or inclusion of paths based on our hypotheses.⁵⁶ Once the model is identified, we will test for group differences (i.e. intervention vs. control) in latent constructs and in the paths between these constructs. This method will allow us to estimate the intervention effects on the constructs directly as well as their relationships to one another.⁵⁶ We will follow guidelines for adequate reporting of SEM using three goodness-of-fit indices: Bentler-Bonnet's Normed Fit Index (NFI), Bentler-Bonnet's Non-Normed Fit Index (NNFI), and the Comparative Fit Index (CFI). We will also verify the root mean-square error of approximation (RMSEA) as an index of misfit. Well-fitting models will have fit indices of .90 or higher and <.06 for RMSEA.

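### The before/after mediator step in section 8.2 is confined to the CareAvenue arm, where the intervention variable is constant, so the coefficient it compares cannot be estimated

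*Combined protocol and SAP*

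**What the plan says.** Section 8.2 of the combined protocol and SAP has two parts that bear on this point.

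- **Outcome model.** The exposure is binary: "The model will have the intervention (yes/no) as the main independent" variable. HbA1c is modelled with "fixed effects for the treatment arm (the intervention group vs. the control group"), a period term (baseline versus the intervention year) and their interaction. The interaction is named as the parameter of interest.
- **Mediation paragraph, first sentence.** The population is set by the opening words: "Among those randomized to CareAvenue in Aim 1, we will assess the change in magnitude of the outcome". The quantity to be compared is then given as that coefficient's "association with the intervention before and after the adjustment of mediators of interest". Figure 1, the conceptual model, is cited for the mediators.
- **Mediation paragraph, later sentences.** After a sentence on adding or deleting paths, the third says: "Once the model is identified, we will test for group differences (i.e. intervention vs. control) in latent constructs" and in the paths between them. The fourth adds: "This method will allow us to estimate the intervention effects on the constructs directly as well as their relationships to one another".

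The step serves Aim 2 (section 2), which concerns mediators and moderators of CareAvenue's effectiveness. Engagement is mentioned in section 7.2: "We will measure program engagement by completed IVR calls and web analytics data". That is process evaluation, and section 8.2 does not refer to it.

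**The concern.** Comparing a treatment coefficient before and after mediator adjustment requires a treatment coefficient. The population clause removes the control arm, and with it the only contrast that the yes/no variable carries. The paragraph also points two ways on population: one arm in its first sentence, both arms in its third.

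Aim 2 hypothesises that changes in the mediators are the main route by which glycaemic control improves. If the step is left as written, the analyst must choose a replacement later, possibly with data in hand. If the model is simply run and the software drops the aliased terms, the surviving coefficient is the CareAvenue arm's uncontrolled change from baseline. Three features of the plan make that change a poor stand-in for the intervention effect:

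- Both arms receive text messages for 52 weeks, including a weekly self-rating with feedback (section 6.3.2).
- Control participants receive contact details for the Guest Assistance Program (section 6.1).
- Entry requires a raised recorded HbA1c (section 4.1), so part of any fall may be regression to the mean.

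A mediator that accounts for this change need not account for the difference between arms.

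**Working it through.** The plan gives no figure for this step, so there is none to reproduce. The check is whether the coefficient is identified.

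**Inputs.** The arm variable A is 1 for CareAvenue and 0 for control, and period P is 0 at baseline and 1 in the intervention year (both section 8.2). There are three visits (section 7.1) and 255 participants per arm with outcome data (section 10). The last two set only the matrix dimensions.

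**Algebra.** Leaving out covariates and random effects, the section 8.2 model with a mediator M is

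Y = b0 + b1·A + b2·P + b3·A·P + g·M + error.

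b3 is the randomised effect on change. Setting A = 1 for everyone gives

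Y = (b0 + b1) + (b2 + b3)·P + g·M + error.

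Only the sums b0 + b1 and b2 + b3 can be estimated. Neither b1 nor b3 can be separated out, with or without M. What remains, b2 + b3, is the control-type change over time plus the intervention effect. A shift in that sum after adding M cannot be attributed to b3. Adding covariates or random effects does not help, because A still equals the intercept column and A·P still equals the P column.

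**Numerical check.** The rows are 255 × 3 = 765 for CareAvenue alone and 510 × 3 = 1530 for both arms. P is 0 at baseline and 1 at 6 and 12 months, and M is one simulated mediator.

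| Fixed effects | CareAvenue arm only | Both arms |
|---|---|---|
| 1, A, P, A·P | rank 2 of 4 | rank 4 of 4 |
| 1, A, P, A·P, M | rank 3 of 5 | rank 5 of 5 |
| 1, A (one visit) | rank 1 of 2 | rank 2 of 2 |
| 1, A, M (one visit) | rank 2 of 3 | rank 3 of 3 |

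The variance of A is 0 in the CareAvenue arm. With equal arms it is 0.5 × 0.5 = 0.25. The rank deficit is two columns in the longitudinal model and one in the single-visit model. It disappears when the control arm is included, and it does not depend on sample size or effect size.

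**The case against.** The best counter-argument is that the yes/no coding belongs to the preceding paragraph, which describes the outcome model, and that the mediation sentence is loosely worded. Two readings can be estimated within one arm: the period coefficient, and the association of the outcome with engagement, which is recorded and varies between participants. On this view the sentence is ambiguous rather than impossible. The paragraph can also be read as a sequence, with the model developed in one arm and the groups compared afterwards. Since the two-arm structural equation model already addresses Aim 2, a small clarification might be enough.

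Part of this stands. The restriction may be a drafting slip, or engagement may have been meant. A one-arm step followed by a two-arm step is not in itself contradictory. Figure 1 is not visible and could bear on the mediators and their timing.

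The rest does not. Section 8.2 names neither alternative exposure. The only definition of the intervention it gives is CareAvenue versus control, and the visible text cites Figure 1 for the mediators, not for a recoded exposure. Neither alternative gives the randomised effect whose mediation Aim 2 concerns: the period coefficient is an uncontrolled change, and engagement is self-selected. The later two-arm model limits the damage but does not make the earlier step runnable.

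**Conclusion.** The concern holds. As written, the before/after mediator comparison cannot be carried out: in its stated population neither the arm coefficient nor the arm-by-period coefficient is estimable. This rests on one assumption, that the intervention in the mediation sentence is the yes/no variable defined in the same section. No other definition appears in the visible text.

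The scope is narrow: one step of one aim. The primary HbA1c analysis, the sample size and the two-arm structural equation model do not depend on it. It should be fixed because an analysis serving a named aim cannot run as stated and its replacement should not be left open. Confidence is high, since the result follows from the plan's own definitions.

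**What to change.** In the first sentence of the mediation paragraph of section 8.2, replace the restriction to the CareAvenue arm with all randomised participants in both arms. Name the arm-by-period coefficient as the quantity compared before and after mediator adjustment. If an analysis within the CareAvenue arm is also wanted, for example by engagement, state its exposure explicitly and label it exploratory and non-randomised.

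The cost is one clause and no new data collection: "Participants will complete 3 data collection appointments", and section 6.4 schedules the surveys at baseline, 6 and 12 months. That section names resource navigation and uptake, communication, financial management, cost-related non-adherence, perceived financial burden and social risk factors. It names no self-efficacy measure, although Aim 2 relies on one. Section 6.4 says that further measures are in the surveys, so its availability should be checked there.

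An optional refinement is to use 6-month mediators with 12-month HbA1c, adjusted for baseline values and mediator-outcome confounders, and to state that the mediator-to-outcome path is not randomised. The visible text sets no time order. The small cost is reliance on participants seen at both follow-up visits, or on imputation.

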2 OBJECTIVES

The overall objective is to determine the extent to which activating patients to address health-related financial burdens that impact treatment adherence and unmet SDHs improves disease control, and the mechanisms through which primary and secondary outcomes are achieved. The specific aims of the study are listed below.

Aim 1: Determine the effectiveness of CareAvenue relative to usual care in improving glycemic control and patient-centered outcomes such as CRN behaviors and perceived financial burdens. We hypothesize that participants randomized to CareAvenue will have a change in HbA1c (**primary outcome**) compared to usual care. We will measure the change in HbA1c at baseline, 6 months (-2 weeks/+4 weeks), and 12 months (-2 weeks/+4 weeks) using an HbA1c machine. Additionally, we hypothesize that other patient-centered outcomes (**secondary outcomes**) will change compared to usual care. Secondary outcomes will be measured at baseline, 6 months (-2 weeks/+4 weeks), and 12 months (-2 weeks/+4 weeks). They include blood pressure (measured with an automated blood pressure cuff), Cost-related non-adherence behaviors with prescribed treatment regimens related to diabetes, Cost-related non-adherence behaviors with prescribed treatment regimens related to other conditions being managed, Perceived financial burden, and unmet social risk factors.

Aim 2: Examine mediators and moderators of the effectiveness of CareAvenue on primary and secondary outcomes. We hypothesize that the intervention will significantly improve skills and self-efficacy in uptake and use of resources leading to decreased financial burdens, perceived stress of unmet SDHs, and improved adherence to treatment regimens, with these changes being the primary mechanism through which improvements in glycemic control are achieved. We also hypothesize that CareAvenue will be most effective among patients with high need for resources and low self-efficacy in navigating resources at baseline.

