	Cost-related nonadherence behaviors with prescribed treatment regimens related to diabetes	
 Cost-Related Non-Adherence (CRN) Behaviors related to diabetes will be measured at baseline, 6 months, and 12 months by 4-items adapted from the Medicare Current Beneficiary Survey and 2 items adapted from the National Health Interview Survey that look at diabetes. The items are measured with a 4-point Likert scale. Participants answering "often" or "sometimes" to any of the items are indicated as exhibiting CRN.
	Cost-related nonadherence behaviors with prescribed treatment regimens related to other conditions being managed	
 Cost-Related Non-Adherence (CRN) Behaviors related to other conditions being managed will be measured at baseline, 6 months, and 12 months by 4-items adapted from the Medicare Current Beneficiary Survey and 2 items adapted from the National Health Interview Survey that look at other health conditions being managed. The items are measured with a 4-point Likert scale. Participants answering "often" or "sometimes" to any of the items are indicated as exhibiting CRN.
	Perceived financial burden	
 Perceived Financial Burden will be measured at baseline, 6 months, and 12 months by the 12-item measure Comprehensive Score for Financial Toxicity (COST) – Functional Assessment of Chronic Illness Therapy (FACIT). The items are measured with a 5-point Likert scale. The higher the score the better the Financial well-being.
	Unmet Social Risk Factors	
 Change in Unmet Social Risk Factors will be measured at baseline, 6 months, and 12 months by 20 items adapted from the Accountable Health Communities Health-Related Social Needs Screening Tool, the Health Leads Social Needs Screening Toolkit, and the Kaiser Permanente Your Current Life Situation Questionnaire. The item values are binary (yes/no). Number of "yes" responses indicates number of unmet social risk factors.
	Unmet Social Risk Factors	
 Change in Unmet Social Risk Factors will be measured at baseline, 6 months, and 12 months by 3 items from the Accountable Health Communities Health-Related Social Needs Screening Tool and 1 item adapted from the National Health Interview Survey. The items each have three response options, in which a positive response indicates an unmet social risk factors.

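### Mediation for yes/no outcomes: the before/after coefficient comparison is not limited to linear models, and in logistic models it can shift without mediation, usually hiding it

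*Combined protocol and SAP*

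**What the plan says.** Section 2 sets Aim 2 as "Examine mediators and moderators of the effectiveness of CareAvenue on primary and secondary outcomes". Its mechanism hypothesis centres on HbA1c, "with these changes being the primary mechanism through which improvements in glycemic control are achieved", but the aim itself also takes in the secondary outcomes.

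Table 2 in section 6.4 lists two CRN secondary outcomes, one for diabetes and one for other conditions. Both reduce Likert items to a yes/no class: a frequent enough answer "to any of the items are indicated as exhibiting CRN".

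Section 8.2 proposes a mixed model for HbA1c, a similar approach for the secondary outcomes and, after dichotomising, to "use similar mixed-effects logistic regression models to test differences in HbA1c, CRN behaviors" and the other outcomes. For mediation it will look at how far the outcome coefficient's "association with the intervention before and after the adjustment of mediators of interest" changes in size. That sentence opens "Among those randomized to CareAvenue in Aim 1". The same paragraph goes on to a structural equation model (SEM) with path tests, arm comparisons and fit criteria. It names no link function, estimator or effect scale for a binary outcome. Section 8 also mentions GEE models with inverse probability weighting.

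**The concern.** In a linear model, the fall in the intervention coefficient when a mediator is added equals the indirect effect. In a logistic model it does not. Adding a variable that predicts the outcome generally enlarges the conditional log odds ratio relative to the unadjusted one, even when the intervention does not affect that variable. This shift runs opposite to mediation, so the two partly cancel in a before/after comparison.

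Aim 2 exists to show how the intervention works. If the comparison is applied to CRN or a dichotomised outcome, a working pathway can look weaker than it is, and a variable that mediates nothing can appear to mediate negatively.

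**Working it through.** The documents report no mediation figure, so there is nothing to reproduce. They also give no mediator strength, no CRN rate under the trial's definition and no random-effect variance; those inputs below are assumptions. The pilot's Table 1 gives single-item CRN rates of 9% to 15% at baseline, but not the rate for any item.

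Throughout, A is arm, M is a standardised mediator and apparent share = 1 - b_adjusted / b_unadjusted.

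**Linear outcome.** If Y = a + bA + gM + error and the arm shifts M by d, the coefficient without M is b + gd and with M is b. The change, gd, is the indirect effect. With d = 0 nothing moves.

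**Ordinary logistic model, no mediation.** logit P(Y) = a + bA + ln(OR)·M, M ~ N(0,1) independent of A, b = -0.5. The unadjusted coefficient comes from averaging the risk over M in each arm (numerical quadrature). Example with a = -0.8 and OR 2: risks are 0.327 (control) and 0.235 (intervention), so the unadjusted coefficient is ln(0.235/0.765) - ln(0.327/0.673) = -0.458, and the share is 1 - 0.500/0.458 = -9%.

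| Mediator OR per SD | a = -2.0: control rate; unadjusted b; share | a = -0.8: control rate; unadjusted b; share |
|---|---|---|
| 1.5 | 13%; -0.492; -2% | 32%; -0.485; -3% |
| 2 | 14%; -0.476; -5% | 33%; -0.458; -9% |
| 3 | 16%; -0.435; -15% | 34%; -0.410; -22% |
| 4 | 18%; -0.400; -25% | 36%; -0.374; -34% |

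The true share is 0% in every cell.

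**Ordinary logistic model, real mediation.** a = -0.8, b = -0.35, and the arm shifts M by -0.2 SD. The true share is the natural indirect effect over the total effect, as risk differences. For OR 2 the risks are 0.3266 (control), 0.2604 (direct effect only) and 0.2366 (both), so the share is 0.0238/0.0900 = 26%. The unadjusted coefficient is -0.448, so the comparison reports 1 - 0.350/0.448 = 22%.

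| Mediator OR per SD | Comparison reports | True share |
|---|---|---|
| 1.5 | 16% | 17% |
| 2 | 22% | 26% |
| 3 | 25% | 37% |
| 4 | 26% | 42% |

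A second set of assumptions (control rate 20% or 30%, direct odds ratio 0.7, mediator shift 0.2 or 0.4 SD, mediator OR 2 to 5, log odds scale) gives 22% to 53% by comparison against a counterfactual 28% to 65%. The shortfall is 4 to 22 points. The product of paths, g·d/(g·d + b), stays within 1 point of the counterfactual share.

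**Random-intercept logistic model, no mediation.** This is closer to the model named in 8.2: three visits, the arm-by-period coefficient, intercept SD 1.5, conditional odds ratio 0.5, M unaffected by arm, one simulated data set of 30,000 people per setting, maximum likelihood.

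| Mediator OR per SD | M constant within person | Half its variance within person | All within person |
|---|---|---|---|
| 2 | 0% (-0.708 to -0.708) | -5% (-0.740 to -0.778) | about -10% (-0.702 to -0.768) |
| 3 | 0% (-0.684 to -0.685) | -9% (-0.637 to -0.696) | -16% (-0.578 to -0.672) |

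Brackets give the coefficient without and then with M. When M is constant within person, the random intercept already absorbs it, so the coefficient does not move.

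**The case against.** The strongest reply is that the larger figures come from an ordinary logistic model, while 8.2 names mixed-effects models. That stands as to size: in the random-intercept model the artefact is smaller, and nil for a mediator that does not vary within person. It does not remove the point. Aim 2's mediators (skills, self-efficacy, uptake of resources) are things the intervention is meant to change over the year. If the logistic analysis were instead run by GEE, a marginal model, the ordinary-logistic figures would be the relevant guide.

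Second, the SEM in the same paragraph estimates paths directly, and a product of paths largely avoids the artefact. This is fair. But the SEM is not said to replace the coefficient step, its treatment of binary outcomes is not stated, and no rule is given if the two disagree.

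Third, the text does not expressly tie the coefficient step to the logistic models. CRN also sits mainly upstream of HbA1c in the hypothesised chain, so it may serve more as a mediator than as an outcome. The link is indeed an inference from Aim 2's scope and from the absence of any restriction in 8.2.

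A reader might go further and infer that the mediated share for CRN will be wrong, or that Aim 2's mediation analysis fails as a whole. The documents support neither. No mediated share is planned, only a change in magnitude; the share above is a way of expressing that change. With a weak mediator (OR 1.5) the comparison gives 16% against a true 17%. The central HbA1c mediation is linear.

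**Conclusion.** The point holds as a gap in specification with a possible bias. As written, the coefficient comparison extends to outcomes for which it can mislead, usually by hiding mediation. Its size depends on mediator strength, CRN rate and how much of the mediator varies within person, none of which the documents give. Under the assumptions shown it runs from nil to -16% in a random-intercept model at mediator odds ratios of 2 to 3, and from about -2% to -22% in an ordinary logistic model at 1.5 to 3. HbA1c mediation by linear mixed model and the primary comparison are unaffected.

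The same sentence has a separate and more basic flaw: it confines the step to the intervention arm, where the intervention variable does not vary and no coefficient for it can be estimated. All the calculations above therefore use both arms.

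**What to change.** In section 8.2, limit the before/after coefficient comparison to outcomes analysed by linear mixed models. For CRN and every dichotomised outcome, estimate direct and indirect effects on the risk-difference scale by counterfactual mediation (for example g-computation), using both arms, adjusted for baseline mediator and baseline outcome, with bootstrap intervals. In the same edit, remove the restriction to the intervention arm, and state how the SEM treats binary outcomes and which analysis is read first.

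The cost is a few sentences and some extra programming; no new data are needed. The counterfactual method relies on there being no unmeasured confounding between mediator and outcome, but the coefficient comparison needs that too.

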4.1 Inclusion and Exclusion Criteria

Study participants will meet the following criteria:

- 18-75 years of age
- Have access to a telephone that can receive and send text messages
- diagnosis of diabetes with prescribed anti-hyperglycemic medication
- most recent (within the past 6 months) recorded hemoglobin A1c (HbA1c) level of $\geq 7.5\%$ for individuals ≤ 70 years and $>8.0\%$ for individuals between 70-75 years in age
- positive report of financial burden or CRN using screening questions developed and validated from prior work³³⁻³⁷

Exclusion criteria include significant cognitive impairment precluding individuals from completing the study as evidenced by ability to complete study intake procedures and current participation in another diabetes study.

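### The Aim 2 mediation step is limited to one arm, where no intervention coefficient exists, and leaves open how mediators enter the model; entered as observed, they can show mediation that is not there

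*Combined protocol and SAP*

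**What the plan says.** Aim 2 (Section 2, Objectives) names improved skills and self-efficacy, lower burden and stress, and better adherence, "with these changes being the primary mechanism through which improvements in glycemic control are achieved". The hypothesis is therefore about change.

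Section 8.2 defines one HbA1c model: "we will fit a longitudinal mixed-effects model to all repeated measurements during the pre-randomization baseline period and the one-year intervention period", with arm, period and their interaction, adjusted for age, gender, race, income, insurance type, comorbidities and health literacy. The interaction is the parameter of interest. On the random part it says only "Random effects are included in the model to adjust for HbA1c variation over time within patients".

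The mediation step follows. "Among those randomized to CareAvenue in Aim 1", the plan compares the size of the outcome coefficient's "association with the intervention before and after the adjustment of mediators of interest (see Figure 1, conceptual model". The same paragraph then moves to structural equation modelling: "we will test for group differences (i.e. intervention vs. control) in latent constructs and in the paths between these constructs".

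Section 8.2 does not say whether a mediator enters as observed, centred, lagged or adjusted for baseline. It gives no rule for concluding that mediation is present.

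**The concern.** There are two problems in one sentence.

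First, among CareAvenue participants the arm indicator is constant and the arm-by-period term is identical to period. No intervention coefficient can be estimated, before or after adjustment. All that remains is pre-post change, which is not a randomized contrast.

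Second, suppose the step is run in both arms with the observed mediator added as a covariate. The arm-by-period effect is a contrast of changes within patients, but the mediator has a single slope. A random intercept does not separate the within- and between-patient associations in that slope, because it assumes that the patient effect is unrelated to the mediator. Patients with more burden or more cost-related non-adherence may have higher HbA1c for lasting reasons. Section 6.4 measures depressive symptoms and diabetes distress, and neither is among the seven covariates. Any mediator that CareAvenue shifts, and that also marks such patients, would then appear to carry part of the HbA1c effect. What is at stake is the mechanism claim of Aim 2. The Aim 1 comparison is not affected.

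**Working it through.** The documents give no figure for the mediation analysis, so there is none to reproduce.

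**Inputs from the documents.** 255 per arm with outcome data (510 in total), SD 1.46 and difference 0.53 (Section 10); three visits (Section 6.1). The standard two-means formula with 0.53, SD 1.46 and 80% power gives about 120 per arm, not 255. That is a separate matter, and 255 is used here as stated.

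**Assumed inputs.** True within-patient mediator effect zero; ICC 0.6 for HbA1c (Y) and for the mediator (M, scaled to SD 1); CareAvenue shifts M by 0.4 SD; patient-level correlation r between M and HbA1c after covariates, from 0 to 0.5 and signed so that the mediator looks causal; mediation declared if both the arm-to-mediator and mediator-to-HbA1c paths have p<0.05.

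**Pooled slope of the observed mediator**

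- Weight on between-patient information: λ = (1−ICC_Y)/[(1−ICC_Y)+3·ICC_Y] = 0.4/(0.4+1.8) = 0.182.
- Within-patient information per patient: W = 2(1−ICC_M) = 0.8.
- Between-patient information: B = 3[ICC_M+(1−ICC_M)/3] = 2.2, so λB = 0.4.
- Between-patient slope: r·√(ICC_Y·ICC_M)·1.46/[ICC_M+(1−ICC_M)/3] = r × 0.876/0.733 = 1.195r.
- Pooled slope, with within-patient slope zero: λB × 1.195r/(W+λB) = 0.4 × 1.195r/1.2 = 0.398r.
- SE: √[0.4 × 1.46²/(510 × 1.2)] = √(0.8526/612) = 0.0373.
- False share: 0.4 × slope/0.53.

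The arm-to-mediator path has SE √(2 × 0.4 × 1.5/255) = 0.0686 and z = 0.4/0.0686 = 5.8. It is almost always significant, so the slope test decides.

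| r | slope | z | both paths p<0.05, formula | same, simulated | false share |
|---|---|---|---|---|---|
| 0 | 0 | 0 | 5% | about 5% | 0% |
| 0.1 | 0.040 | 1.07 | 19% | about 17% | 3% |
| 0.2 | 0.080 | 2.13 | 57% | about 60% | 6% |
| 0.3 | 0.119 | 3.20 | 89% | about 92% | 9% |
| 0.5 | 0.199 | 5.33 | 100% | 100% | 15% (16% simulated) |

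Separate simulations with different estimators gave 55-61% at r = 0.2 and 90-93% at r = 0.3.

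**Sensitivity at r = 0.3**

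- HbA1c ICC 0.8, mediator ICC 0.4: λ = 0.2/2.6 = 0.077, W = 1.2, λB = 0.077 × 1.8 = 0.138. Slope = 0.138 × 0.413/1.338 = 0.043, SE 0.025, z = 1.71. The rate is 40% by formula and about 43% simulated.
- HbA1c ICC 0.4, mediator ICC 0.8: nearly 100%.
- Both ICCs 0.6, shift 0.2 SD: z for the arm path is 0.2/0.0686 = 2.9, power 83%. The joint rate is about 0.83 × 0.89 = 74%.
- No effect of CareAvenue on the mediator: 0-7% across the correlations and ICCs tried.

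**Deviation term only.** The expected slope is zero when there is no true mediation. SE = √[0.8526/(510 × 0.8)] = 0.0457. Simulated false declaration was 4-6% at ICC 0.6 and 1-8% over all settings tried. Adding only the baseline mediator lowered the rate to 10% at r = 0.2 and 17% at r = 0.3. Those figures rest on 60 runs each, and the same check gave 8% at r = 0, so they are rough.

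**The case against.** The strongest reply is that the criticised model is not in the documents. Section 8.2 never says that the random effect is an intercept only, that the mediator enters at its observed value, or that significance decides. This stands. The second problem is one of underspecification, with consequences that depend on how the gap is filled.

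A reader might infer that the plan would declare false mediation in more than half of trials. The documents do not support that. Such rates need a residual correlation of about 0.2 or more, a real effect on the mediator and a joint-significance rule, none of which the documents give. The correlation that matters is the one left after seven covariates, including income and comorbidities, and it may be small. On the plan's own metric, the change in the coefficient, the distortion is modest.

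A reader might also infer that the whole mediation analysis ignores the control arm. The SEM sentence, which compares intervention with control, contradicts that; the restriction applies to the coefficient comparison. The SEM does not settle the second problem, however. Nothing in its description separates stable differences from change, and fit indices do not test for this. The simulations do not cover the SEM, so no error rate is claimed for it.

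Finally, the split is one option among several: change scores, patient fixed effects or a latent-change SEM would also target within-patient change. That is fair. The plan needs to commit to one of them.

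**Conclusion.** The point holds in two parts. The coefficient comparison cannot be carried out as worded, because it is confined to one arm; this needs no assumptions. In addition, the Aim 2 estimator is undefined, and its natural implementation does not isolate the change that Aim 2 describes. Under the stated assumptions, false declarations run from about 5% to 100% as the residual between-patient correlation goes from 0 to 0.5. Other ICCs move the rate either way at a given correlation, and smaller shifts lower it. The false mediated share is about 3-16% over correlations of 0.1 to 0.5, so the main risk is a mechanism claimed where there is none, more than a large misstatement of its size. This should be corrected before the Aim 2 analysis; it does not touch the primary HbA1c comparison.

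**What to change.** In Section 8.2:

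1. Run the mediation step in both arms and remove the restriction to CareAvenue participants.
2. State the random-effects structure. Enter each mediator as two terms: the patient's mean across visits and the visit's deviation from that mean.
3. Define the indirect effect as the arm effect on the mediator times the deviation slope, with a bootstrap confidence interval, and state that this interval decides. Report the between-patient slope as descriptive only.
4. Specify the SEM so that its paths also concern within-patient change.

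The cost is SAP wording and one extra term per mediator. Where a mediator is collected at the baseline, 6- and 12-month surveys, no new data are needed. The price is precision: at ICC 0.6 the mediator-slope SE rises from 0.037 to 0.046, about a quarter. It rises more for a very stable mediator: with mediator ICC 0.8 and HbA1c ICC 0.4, W = 0.4 and λB = 0.333 × 2.6 = 0.867, so the ratio is √(1.267/0.4) = 1.78.

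The split does not remove time-varying confounding or reverse causation. Because the patient mean uses all visits, a 6-month deviation depends partly on the 12-month value. Both limits belong in the SAP text.
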